5.1.1 Identification

Saxagliptin 5 mg tablets and placebo tablets are plain, yellow, biconvex, round, film coated tablets.

5.1.2 Packaging and Labeling

Saxagliptin film-coated tablets in strengths of 1 mg, 2.5 mg, 5 mg, and 10 mg (as the free base) have been developed. The tablets are manufactured from saxagliptin and inactive ingredients including lactose, microcrystalline cellulose, croscarmellose sodium, magnesium stearate, and film-coating materials (Opadry® II white and Opadry® II yellow). The tablets are supplied in high-density polyethylene bottles containing two desiccant and charcoal canisters, with cotton coil and tightly closed with a child resistant cap.

5.1.3 Storage, Handling, and Dispensing

The investigational product should be stored in a secure area according to local regulations. The investigator is responsible for ensuring that it is dispensed only to study subjects and only from official study sites by authorized personnel, as dictated by local regulations.

Saxagliptin tablets should be stored at temperatures between 20°C and 25°C (68°F and 77°F) in tightly closed containers. The investigator is responsible for ensuring that the investigational product is stored under the appropriate environmental conditions (temperature, light, and humidity), as determined by the sponsor.

If concerns regarding the quality or appearance of the investigational product arise, do not dispense the investigational product, and contact BMS immediately.

5.2 Drug Ordering and Accountability

5.2.1 Initial Orders

Contact the BMS protocol manager for information.

5.2.2 Re-Supply

Contact the BMS protocol manager for information.

5.3 Method of Assigning Subjects to a Treatment

Patients will be randomized to one of the two treatment groups i.e. saxagliptin or placebo. Randomisation numbers (patient numbers) will be assigned strictly sequentially

as patients become eligible for randomisation. Randomization will be computer-generated by the research pharmacy, and the investigators will be blinded to the treatment assignments. The research pharmacy will provide the randomisation number and the appropriate bottle numbers.

5.4 Selection and Timing of Dose for Each Subject

The recommended dose of saxagliptin is 5 mg once daily. Saxagliptin can be taken with or without food. We shall administer saxagliptin 5 mg once daily PO for 6 months.

5.5 Blinding/Unblinding

Blinding is critical to the integrity of this clinical study. However, in the event of a medical emergency or pregnancy in a subject, **in which knowledge of the investigational product is critical to the subject's management**, the blind for that subject may be broken by the treating physician.

Before breaking the blind of an individual subject's treatment, the investigator should have determined that the information is necessary, ie, that it will alter the subject's immediate management. In many cases, particularly when the emergency is clearly not investigational product-related, the problem may be properly managed by assuming that the subject is receiving active product without the need for unblinding.

5.6 Concomitant Treatments

5.6.1 Prohibited and/or Restricted Treatments

The co-administration of saxagliptin and strong CYP3A4/5 inhibitors such as ketoconazole, atazanavir, clarithromycin, indinavir, itraconazole, nefazodone, nelfinavir, ritonavir, saquinavir, and telithromycin may result in increased plasma concentrations of saxagliptin and should be avoided.

5.6.2 Other Restrictions and Precautions

Saxagliptin should not be used in patients with type 1 diabetes mellitus or for the treatment of diabetic ketoacidosis.

5.7 Treatment Compliance

Treatment compliance will be monitored by drug accountability as well as the patient's medical record.

6 STUDY ASSESSMENTS AND PROCEDURES

6.1 Time and Events Schedule

Table 1: Time and Event Schedule for Protocol [Insert Protocol Number]

Procedure	Visit 1 (Screening)	Visit 2 (OGTT)	Visit 3 (Pre randomization)	Visit 4 (Randomization)	Visit 5	Visit 6	Visit 7	Visit 8	Visit 9	Visit 10	Visit 11
Study week	-4	-2	-1	0	2	6	10	14	18	22	26
Obtain Informed Consent	X										
Confirm Eligibility	X										
Medical History	X										
Review Concomitant	X		X		X	X	X	X	X	X	X
Physical Examination	X				X	X	X	X	X	X	X
Vital Signs	X		X		X	X	X	X	X	X	X
Run 12-Lead Electrocardiogram	X										
Diet Counseling		X									
Pregnancy Test (a)	X		X		X	X	X	X	X	X	X
Urinalysis	X										
CBC, Lipids, LFTs, Serum Creatinine	X							X			X
FPG	X		X		X	X	X	X	X	X	X
HbA1c	X		X					X			X
OGTT		X									X

Insulin/Cytokines/FFA			X								X
Monocyte isolation			X								X
MRI Studies			X								X
Randomize				X							
Study drug				Start	x	x	x	x	x	x	Stop
Medication Compliance Check					X	X	X	X	X	X	X
Assess for Adverse Events		X	X	X	X	X	X	X	X	X	X

6.2 Study Materials

Bristol-Myers Squibb (BMS) will provide saxagliptin at no cost for this study.

6.3 Safety Assessments

Study drug toxicities will be assessed continuously. Adverse events will be evaluated on a continuous basis while the patient is on study and until 30 days after the last dose of study drug. Patients should be followed until all treatment-related adverse events have recovered to baseline or are deemed irreversible by the principal investigator. Patients will report every 4 weeks while on the study drug and a complete safety assessment including a complete history and physical and fasting blood glucose will be performed to evaluate for the following specific adverse events

- Headache, URI, nasopharyngitis

-Nausea, abdominal discomfort, gastroenteritis

-Hypersensitivity-related reactions including skin rash (rare)

-Hypoglycemia (mild to moderate). Treatment with saxagliptin led to rates of hypoglycemia that were generally similar compared with placebo. This is consistent with the mechanism of action of DPP-IV inhibitors, which exert their insulinotropic effects on the β cell in a glucose dependent manner. Severe hypoglycemia has not been reported in patients on saxagliptin monotherapy.

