APPENDIX 1: *None*

PROTOCOL SYNOPSIS

Protocol Title:	Effect of Saxagliptin Treatment on Myocardial Fat Content, Left Ventricular Function, and Monocyte Inflammation in Patients with Impaired Glucose Tolerance
Site Numbers & Names:	Baylor College of Medicine, Houston, TX
Research Hypothesis:	We hypothesize that saxagliptin therapy (compared to placebo) would be associated with a reduction in myocardial and hepatic fat content, an improvement in left ventricular (LV) function, and a reduction in monocyte inflammation in patients with impaired glucose tolerance.
Study Schema: Drugs / Doses / Length of Treatment)	Saxagliptin 5 mg or placebo PO daily for 6 months
Study Objectives: 
• Primary:• Secondary:	The primary objective is to examine the effects of saxagliptin on myocardial and hepatic fat content in patients with impaired glucose tolerance (IGT). The secondary objective is to examine the effect of saxagliptin on left ventricular systolic and diastolic function and monocyte inflammation in patients with IGT.
Study Design:	Patients with IGT or prediabetes will be randomized to receive saxagliptin or placebo in a double blind placebo controlled single center trial.
Accrual Goal: (Total number of subjects)	40 patients
Accrual Rate: (Number of subjects expected per month)	3 patients per month
FPFV: LPFV: Follow Up: (dd-mm-yy)	December 1, 2011 December 1, 2012 31-05-2013
Correlative Studies: (PK/PD, etc.)	-
Inclusion Criteria:	Patients between the age of 30 and 70 years with IGT.

Exclusion Criteria:	Patients with type 1 or type 2 diabetes and patients on any anti-hyperglycemic medications
Criteria for Evaluation: (Efficacy, safety, stopping rules, etc.)	Changes in myocardial and hepatic fat, LV function and monocyte inflammation following saxagliptin versus placebo treatment for 6 months.

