4.3 Data Safety Monitoring Plan

Protocol and consent form approval has been obtained from the Baylor College of Medicine IRB. Request for IND shall be submitted to the FDA. Prior to screening evaluations, each subject eligible for the study will be given an orientation session in which the nature and purpose of the study and the risks and benefits will be described. If an eligible subject agrees to participate in the study, he/she will be required to sign an informed consent form.

The PI and his team will monitor the study on a daily basis. All treatment emergent AEs will be recorded on source documents (i.e. original documents, data, and records). AEs include those reported spontaneously by the subject and those noted incidentally or as observed by the investigator or study personnel. All clinically significant abnormalities noted upon physical examination, or other diagnostic test results should be reported as an AE, except for baseline measurements that may be considered part of the medical history. In addition, all clinically significant AEs that continue at Study Termination will be followed up by the investigator and evaluated with additional tests if necessary, until the underlying cause is diagnosed or resolution occurs. All AEs will be evaluated for intensity and causal relationship with use of the study medication and/or study procedures by the investigator and reported to the Baylor IRB. All SAEs will be reported to the Baylor IRB and the sponsor within 24 hours. In addition, a safety report will be submitted to Baylor IRB annually. Any new information regarding saxagliptin will be submitted to Baylor IRB.

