7.3.1 Serious Adverse Events and Adverse Events of Special Interest

Following the subject’s written consent to participate in the study, all SAEs and all AEs of Special Interest (defined in Section 7.1.2), whether related or not related to study drug, must be collected, including those thought to be associated with protocol-specified procedures. All SAEs must be collected that occur during the screening period and within 30 days of discontinuation of dosing. If applicable, SAEs must be collected that relate to any later protocol-specified procedure (eg, a follow-up skin biopsy). The investigator should report any SAE occurring after these time periods that is believed to be related to study drug or protocol-specified procedure.

An SAE report should be completed for any event where doubt exists regarding its status of seriousness.

If the investigator believes that an SAE is not related to study drug, but is potentially related to the conditions of the study (such as withdrawal of previous therapy, or a complication of a study procedure), the relationship should be specified in the narrative section of the SAE Report Form.

All SAEs, whether related or unrelated to saxagliptin, and all pregnancies must be reported to BMS (by the investigator or designee) within 24 hours of study personnel becoming aware of the event. If only limited information is initially available, follow-up reports are required. The original SAE form must be kept on file at the study site.

All SAEs should be reported via confirmed facsimile (fax) transmission, or scanned and reported via electronic mail to:

SAE Email Address: [contact]

SAE [contact]

For studies conducted under an **Investigator IND**, any event that is both serious and unexpected must be reported to the Food and Drug Administration (FDA) as soon as possible **and no later than 7 days** (for a death or life-threatening event) **or 15 days** (for all other SAEs) **after the investigator's or institution's initial receipt of the information.** The investigator must provide BMS with a copy of all adverse events filed with the FDA. SAEs should be reported on MedWatch Form 3500A, which can be accessed at: <http://www.accessdata.fda.gov/scripts/medwatch/>.

MedWatch SAE forms should be sent to the FDA at:

MEDWATCH

[name]

[name]

Fax: [name] ([name])

<http://www.accessdata.fda.gov/scripts/medwatch/>

All SAEs should simultaneously be faxed or e-mailed to BMS at:

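### Adverse events are to be evaluated until 30 days after the last dose, but Table 1 schedules no contact after week 26 at which new events would be elicited

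*Combined protocol and SAP*

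**What the plan says.** The duty is stated twice. Section 6.3 (Safety Assessments): "Adverse events will be evaluated on a continuous basis while the patient is on study and until 30 days after the last dose". Section 7.3.1, on serious adverse events: "All SAEs must be collected that occur during the screening period and within 30 days of discontinuation of dosing".

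The schedule is in section 6.1. In Table 1 the row "Assess for Adverse Events" is marked from Visit 2 to Visit 11. Visit 11 is at study week 26, the study-drug row reads Stop in that column, and there is no later column. Section 6.3 ties the regular visits to treatment: "Patients will report every 4 weeks while on the study drug".

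Two sentences in section 4.3 (Data Safety Monitoring Plan) bear on the time after treatment. One concerns events that are still open: "all clinically significant AEs that continue at Study Termination will be followed up by the investigator". The other accepts unprompted reports: "AEs include those reported spontaneously by the subject and those noted incidentally or as observed by the investigator or study personnel". Section 4.2.3 sends patients who discontinue to the follow-up procedures of section 6. It exempts only those who withdraw consent for all study procedures or lose the ability to consent freely.

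**The concern.** The protocol sets a 30-day window after the last dose but gives site staff no occasion to use it. On treatment, patients are asked about events at scheduled visits. After week 26 a patient with no open event is not asked again, so detection moves from elicited to spontaneous reporting at the point where the window begins.

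At stake is the completeness of the safety data in the protocol's own window. That includes serious events and the events of special interest in section 7.1.2, such as pancreatitis, angioedema and liver abnormalities with jaundice, which are reportable to the company supplying the drug whether or not they are serious. The outputs that could be affected are the descriptive safety summaries in sections 8.3 and 8.4.3.

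**Working it through.** **Inputs.** Treatment lasts 26 weeks (section 4.1). Visits after randomisation fall at weeks 2, 6, 10, 14, 18, 22 and 26 (Table 1). The window is 30 days after the last dose (sections 6.3 and 7.3.1). The plan is to enrol 40 patients so that 32 complete, about 16 per group (section 8.1).

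**Scheduled assessments, counting the first dose as day 0.**
- Week × 7 gives days 14, 42, 70, 98, 126, 154 and 182, which is 7 adverse-event assessments. The first gap is 14 days and each later gap is 28 days.
- Last scheduled assessment: 26 × 7 = day 182.
- End of window for a patient dosed to week 26: 182 + 30 = day 212, or 212 / 7 = week 30.3.
- Scheduled assessments after day 182 and up to day 212: 0.

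**Does any other clause supply a contact?**
- Section 6.3 follows treatment-related events until recovery or until judged irreversible. The event must already be known.
- Section 4.3 follows clinically significant events that are still continuing when the study ends. The event must already be known.
- Section 7.3.1 follows serious events to resolution or stabilisation, and pregnancies to outcome. These must already be known.
- Section 7.3.3 follows nonserious events to resolution, including those that led to stopping drug or were present at the end of treatment. These must already be known.
- Section 4.2.3 refers patients who discontinue to section 6, which lists no contact after treatment beyond the Table 1 visits.
- Section 4.3 accepts spontaneous reports, but that schedules nothing.

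Sections 7.1 and 7.3 say that events are either reported spontaneously or elicited by open-ended questioning, examination or evaluation. Elicitation needs a contact. With none scheduled after day 182, a completer with no open event is left with spontaneous reporting only.

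**Sensitivity of the summaries, as an illustration only.** One further patient with an event changes an arm's percentage by 1/16 = 6.25 points among 16 completers, or by 1/20 = 5 points among 20 randomised patients (assuming 40 are split equally). This shows how coarse the summaries are. It does not predict how many events would be missed.

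**The case against.** The strongest reply is that the sections do not contradict each other. Section 6.3 itself lies in section 6 and imposes the duty, and section 7.3.1 makes collection of serious events mandatory over the same window and asks for related ones after it. Table 1 lists study visits, and the lack of a telephone column cancels nothing. Later contact is not forbidden. On this view only the mode of contact is unspecified. Most of this stands: the reporting obligation is intact and there is no loss of duty. It does not remove the gap, because a duty to evaluate continuously for 30 days is not met by waiting for patients to call, and the protocol names no other means for completers.

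It is also fair to say that sections 8.3 and 8.4.3 give no counting window, and that section 4.3 speaks of treatment-emergent events. Whether events after week 26 would enter the summaries is therefore not settled.

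A reader might infer more than the documents support in three ways.
- **That the synopsis dates confirm an intention to end follow-up with treatment.** The synopsis gives "December 1, 2011 December 1, 2012 31-05-2013" for FPFV, LPFV and follow-up. LPFV is not defined. If it is the first-dose day, week 26 is June 1, 2013, next to the stated date. If it is the week −4 screening visit, week 26 is June 29, 2013, and the stated date falls before treatment ends. The dates also look out of date: the inclusion criteria cite a 2014 reference, and the synopsis statistics entry still enrols 36 patients against 40 in section 8.1. They say nothing reliable about safety follow-up.
- **That patient-days without contact measure harm.** Multiplying 30 days by the number of completers only restates the length of the window.
- **That early discontinuers must keep all remaining Table 1 visits.** That is a separate retention question. Those visits include MRI, OGTT and monocyte isolation, so they carry their own cost, and this point does not depend on the answer.

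**Conclusion.** The point holds as a small and inexpensive improvement to safety ascertainment. Sections 6.3 and 7.3.1 require 30 days of evaluation and collection after the last dose. Table 1 provides 7 assessments after the first dose up to day 182 and none in the following 30 days. New events in completers during that window would depend on spontaneous report.

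The gap is the same in both arms by design, in a trial the synopsis describes as a "double blind placebo controlled single center trial". It has no effect on the efficacy analyses. The number of missed events cannot be estimated from the documents. The conclusion rests on two readings: that Table 1 is the full list of scheduled contacts, and that continuous evaluation means more than accepting unprompted reports.

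**What to change.** Add one column to Table 1 after Visit 11, headed *AE contact (telephone) 30 days after last dose*, with the adverse-event row marked. Apply it to completers and to early discontinuers, except those who have withdrawn consent for all procedures or lost the ability to consent freely, which keeps the exception already in section 4.2.3. Use the open-ended questioning that sections 7.1 and 7.3 prescribe. Add a sentence to section 4.2.3 pointing to the new column, so that its reference to section 6 leads to a named procedure.

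The cost is one call per patient, so at most 40 calls by existing staff at a single site, plus one table column and one sentence. No follow-up time is added, because sections 6.3 and 7.3.1 already require the 30 days. For an early discontinuer who keeps coming to visits the call adds little, but one rule for everyone is simpler to run.

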6.4 Efficacy Assessments

6.4.1 Primary Efficacy Assessment

The primary efficacy objective is to determine whether treatment with saxagliptin compared with placebo will result in a reduction in hepatic and myocardial fat in patient with IGT.

6.4.2 Secondary Efficacy Assessments

The secondary efficacy objective is to determine whether treatment with saxagliptin compared with placebo will result in an improvement in left ventricular systolic and diastolic function and a reduction in monocyte inflammation in patients with IGT.

7 ADVERSE EVENT REPORTING

7.1 Adverse Events

An *Adverse Event (AE)* is defined as any new untoward medical occurrence or worsening of a pre-existing medical condition in a patient or clinical investigation subject administered an investigational (medicinal) product and that does not necessarily have a causal relationship with this treatment. An AE can therefore be any unfavorable and unintended sign (including an abnormal laboratory finding, for example), symptom, or disease temporally associated with the use of investigational product, whether or not considered related to the investigational product.

Adverse events can be spontaneously reported or elicited during open-ended questioning, examination, or evaluation of a subject. (In order to prevent reporting bias, subjects should not be questioned regarding the specific occurrence of one or more AEs.)

7.1.1 Serious Adverse Events

A *Serious Adverse Event (SAE)* is any untoward medical occurrence that at any dose:

- results in death
- is life-threatening (defined as an event in which the subject was at risk of death at the time of the event; it does not refer to an event which hypothetically might have caused death if it were more severe)
- requires inpatient hospitalization or causes prolongation of existing hospitalization (see note below for exceptions)
- results in persistent or significant disability/incapacity
- is a congenital anomaly/birth defect
- is an important medical event, defined as a medical event that may not be immediately life-threatening or result in death or hospitalization but, based upon appropriate medical and scientific judgment, may jeopardize the subject or may require intervention (eg, medical, surgical) to prevent one of the other serious outcomes listed above. Examples of such events include but are not limited to intensive treatment in an emergency department or at home for allergic bronchospasm; blood dyscrasias or convulsions that do not result in hospitalization. **Potential drug induced liver injury (DILI) is also considered an important medical event (see Section 7.7 for the definition of potential DILI)**

Suspected transmission of an infectious agent (eg, any organism, virus or infectious particle, pathogenic or non-pathogenic) via the study drug is an SAE.

Although pregnancy, overdose, and cancer are not always serious by regulatory definition, these events must be handled as SAEs for data transmission purposes (See Section 7.5.2 for reporting pregnancies).

NOTE: The following hospitalizations are not considered SAEs in BMS clinical studies:

- a visit to the emergency room or other hospital department lasting less than 24 hours that does not result in admission (unless considered an “important medical event” or a life-threatening event)
- elective surgery planned before signing consent
- admissions as per protocol for a planned medical/surgical procedure
- routine health assessment requiring admission for baseline/trending of health status (eg, routine colonoscopy)
- medical/surgical admission for purpose other than remedying ill health state that was planned before study entry. Appropriate documentation is required in these cases.
- admission encountered for another life circumstance that carries no bearing on health status and requires no medical/surgical intervention (eg, lack of housing, economic inadequacy, caregiver respite, family circumstances, administrative).

